From the 22nd February 2021, a national pathway for vaccination for pregnant women was clarified, with information leaflets provided for women, and on the 9th March pregnant women with current gestational diabetes were added to the list of individuals clinically vulnerable to severe COVID-19 disease, making this group of women eligible for vaccination. On the 16th April 2021, the JCVI issued further guidance, confirming that women called for vaccination due to being in any priority group (including all adults aged 18-49 years) could be offered vaccination during pregnancy. The JCVI recommendation issued on 16 April 2021 remains unchanged and therefore women who are pregnant should be offered vaccination at the same time as non-pregnant women, based on their age and clinical risk group. At the time of the last JCVI recommendation, most of the safety data on vaccination in pregnancy related to the use of the Pfizer–BioNTech (Comirnaty) and Moderna (Spikevax) vaccines; consequently, the JCVI recommended that pregnant women in the UK should be offered the Pfizer/BioNTech or Moderna vaccine if stocks of those vaccines were available. However, as there is no evidence to suggest that other vaccines are unsafe for pregnant women, all the approved vaccines can be given in pregnancy. For example, if a woman had a first dose of vaccine prior to pregnancy, she should complete her course with the same vaccine if possible, regardless of vaccine type.

As COVID-19 vaccines are now being offered routinely to pregnant women in Scotland, it is necessary to monitor the safety of these vaccines in this population. This protocol details the technical specification for the assessment of the safety of COVID-19 vaccines in pregnant women in Scotland. This will be done through monitoring a series of pre-specified pregnancy, maternal and neonatal outcomes. Specifically, we will monitor whether the risk of these outcomes is different among vaccinated pregnant women compared to unvaccinated pregnant women.

2.0: Objectives

The main aim of this work is to assess the safety of receiving COVID-19 vaccines during pregnancy. This will be achieved through the following objectives:

1. To estimate the risk of adverse pregnancy, maternal and neonatal outcomes in vaccinated and unvaccinated pregnant women.
2. To investigate whether the risk of adverse pregnancy, maternal and neonatal outcomes is different in vaccinated pregnant women, compared with unvaccinated pregnant women.

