
Datasets required to identify vaccinated individuals
	
 • Data from the National Clinical Data Store (NCDS). Information recorded on the National Vaccine Management Tool (VMT) and GPIT system (Primary care practice medical record database) flows to the

² Stock SJ, McAllister D, Vasileiou E, *et al.* COVID-19 in Pregnancy in Scotland (COPS): protocol for an observational study using linked Scottish national data. *BMJ Open* 2020;**10**:e042813. doi: 10.1136/bmjopen-2020-042813. Available from: [COVID-19 in Pregnancy in Scotland \(COPS\): protocol for an observational study using linked Scottish national data | BMJ Open](#)

	NCDS, from where it is cleaned and then linked to the COPS data. Relevant data of interest: vaccination date, type, dose.
Datasets required to identify outcomes of interest	
 Data from a number of sources that hold pregnancy, maternal and neonatal outcome data will be brought into the COPS study dataset. Sources include: SMR01, SMR02, national linked anomaly database, SICSAG critical care admissions, NRS deaths.

3.5: Study Variables

3.5.1: Study Outcomes

Maternal, pregnancy and neonatal outcomes of interest are listed in Table 2. In our main analyses, we will assess the risk of each outcome in vaccinated women and their unvaccinated controls (i.e. classifying each woman as having the outcome or not), and will not attempt to capture any differences between the groups in the time to these events. As noted in Table 2, there are different periods of risk for each outcome (referred to as “outcome-specific follow-up period” throughout this protocol). For example, women will be considered at risk of any miscarriage from conception up to 23⁺⁶ weeks gestation, and at risk for stillbirth from 24⁺⁰ weeks gestation to the end of pregnancy. Women without an observed outcome who had not completed follow-up to the end of the follow-up period for a specific outcome in either the pre-pandemic (i.e. outcome-specific follow-up period not completed before 01 March 2020) or in the pandemic time period (i.e. outcome-specific follow-up period not completed before date of data extraction) will not be eligible for inclusion in the analysis for that outcome.

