*Note that only women who have been followed-up to the end of the outcome-specific follow-up period at the end of each study period (i.e. 29 February 2020 for pre-pandemic controls and data of data extraction for pandemic controls) are eligible to be controls for a given outcome analysis.

3.7: Power calculation for matched cohort

It is estimated that by the end of 2021, full outcome and follow-up data will be available for approximately 5,000 vaccinated pregnant women, and by end of 2022, data available for 10,000 vaccinated pregnant women⁶.

Outcomes can be grouped as frequent (risk approximately 10%), moderate (approximately 3%), and rare (approximately 0.5%). Risk estimates for each adverse outcome are provided in Table 2. Based on these estimates and assumptions, with the relative risk of an event occurring post-vaccination set at 0.5, 1.2 and 2.0, and with statistical significance set at 0.05 and 0.01; power calculations for the various scenarios were calculated and are shown in Table 6. The power to detect a relative risk of 0.5, based on 5000 vaccinated pregnant woman against 15000 controls (ratio 1:3), when estimated

⁶ Personal communication with [name], July 2021.

adverse event occurrence is 0.5%, is 94%. This means that the study has a 94% chance of having a p-value of less than 5% (a statistically significant result and strong evidence against the null hypothesis) if there is really a difference in risk between vaccinated and unvaccinated women.

If the statistical power is low, the study sample size may be too small to detect any differences (i.e. under-powered) and therefore null results will need to be interpreted with caution. By convention, 80% is an acceptable level of power. It is acknowledged that the study may be under-powered to identify rarer outcomes.

Table 6: Power calculations scenarios

Cases	Controls	Estimated risk	Relative risk	Power %
5000	15000	0.50%	0.5	94
			1.2	10
			2.0	66
		3.00%	0.5	100
			1.2	45
			2.0	100
		10.00%	0.5	100
			1.2	94
			2.0	100
10000	30000	0.50%	0.5	100
			1.2	17
			2.0	94
		3.00%	0.5	100
			1.2	75
			2.0	100
		10.00%	0.5	100
			1.2	100
			2.0	100

4.0: Data Analyses

4.3: Descriptive analyses

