Characteristics (e.g. covariates) of the vaccinated and unvaccinated cohorts (from the pre-pandemic and pandemic vaccination time periods), and of the number and risk of all outcome events in the vaccinated and unvaccinated groups will be described to assess the comparability of the groups and to provide better understanding of the data. Summary statistics on the dose, type and class of vaccination in the vaccinated population will be described. Median, range and inter-quartile range of the gestational week of vaccination will be calculated.

Summary statistics and plots of time from vaccination (or matching) to date of outcome will be conducted to provide additional contextual information and to explore plausibility of gaps or clustering of the outcomes in time. As this will not be a time-to event analysis, it will be important to explore descriptively whether there are differences in the temporal trends of the outcomes by vaccination status.

Summary tables of the number and risk of each outcome in the vaccinated and unvaccinated pregnant cohorts, overall, by covariates, and by vaccine type, class, dose number, will be produced.

4.4: Statistical analyses

Maternal, pregnancy and neonatal outcomes in the vaccinated and unvaccinated pregnant cohorts will be compared using conditional logistic regression, where possible. This model type is used to account for matching. Odds ratios (ORs) with 95% confidence intervals will be produced for each comparison and a correction for multiple testing applied (e.g. Benjamini and Hochberg).

The exception will be for pregnancy outcomes where there is a competing risk (i.e. each woman can only have one of these outcomes), such as miscarriage, ectopic pregnancy, termination of pregnancy, stillbirth, and live birth. These will be examined using conditional multinomial logistic regression. The reference for each comparison when examining pregnancy outcomes will be live births (or ongoing pregnancies at a relevant gestation when studying early pregnancy outcomes only). Age, gestational week and season/quarter (when included in the matching strategy) will also be included in the model to account for matching. Termination of pregnancy is not an outcome of interest but it will need to be included in models as a competing risk.

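### Section 4.4 commits only to odds ratios as modelled effects; for the common outcomes, add an adjusted risk ratio and risk difference so that effect size is also given on the risk scale of the objectives

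*Protocol*

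**What the plan says.** Section 2.0 words both objectives as risk. The first is "To estimate the risk of adverse pregnancy, maternal and neonatal outcomes in vaccinated and unvaccinated pregnant women"; the second is "To investigate whether the risk of adverse pregnancy, maternal and neonatal outcomes is different in vaccinated pregnant women, compared with unvaccinated pregnant women". Section 3.5.1 keeps that scale: each woman is classed as having the outcome or not, and "we will assess the risk of each outcome in vaccinated women and their unvaccinated controls".

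Section 3.7 sets the power scenarios "with the relative risk of an event occurring post-vaccination set at 0.5, 1.2 and 2.0", at control risks of 10%, 3% and 0.5%.

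Section 4.4 then names the model (conditional logistic regression, or a conditional multinomial version for competing pregnancy outcomes) and the measure: "Odds ratios (ORs) with 95% confidence intervals will be produced for each comparison". It goes on to plan an unadjusted and an adjusted odds ratio for every outcome. No adjusted risk, risk ratio or risk difference is mentioned.

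Absolute risks do appear in section 4.3, as descriptive tables of the number and risk of each outcome by group, covariate and vaccine. Section 4.5 lists a comparison of observed with expected counts, but only as something to be considered.

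**The concern.** This is a cohort in which inclusion requires either an observed outcome or completed outcome-specific follow-up, so risks and their ratios can be estimated directly. The protocol asks about risk and plans its size on relative risk, then reports the adjusted result only as an odds ratio. The two measures nearly coincide for rare outcomes. Several primary outcomes are not rare: Table 2 gives 10% for hypertensive disorders and for small for gestational age, 10 to 20% for miscarriage, and 30% against pregnancy-related bleeding.

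At stake is the reported size of an effect. At these risks the odds ratio is further from 1 in both directions, so a reader who takes it as a relative risk overstates harm when it is above 1 and protection when it is below 1. Section 6.0 sends results to regulators, programme governance and possible meta-analyses, where adjusted relative and absolute effects are both useful.

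**Working it through.** **Inputs.** Relative risks 0.5, 1.2 and 2.0 come from section 3.7. Background risks come from Table 2: 10% (hypertensive disorders, small for gestational age), 7% (preterm birth), 10 to 20% (miscarriage) and 30% (bleeding row, labelled there as the postpartum haemorrhage figure). The 3% and 0.5% groups come from section 3.7.

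**The plan's own figures.** The protocol gives no conversion between the two scales. Its only figures on the relative-risk scale are the powers in Table 6. A two-sample comparison of proportions (pooled variance, 1:3 ratio, alpha 0.05, assumed two-sided because sidedness is not stated) gives, at 0.5% risk with 5,000 vaccinated, 66.5% for a relative risk of 0.5 (stated 94%) and 94.8% for 2.0 (stated 66%). Inverting the direction of the relative risk reproduces all 18 cells within 2 points. At 0.5% risk the odds ratio and relative risk are almost equal, so the choice of odds ratio does not explain this mismatch. It is a separate matter, and nothing below depends on it.

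**Conversion.** With control risk p and relative risk RR:

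OR = [RR·p / (1 − RR·p)] / [p / (1 − p)]

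Examples:
- p = 0.10, RR = 1.2: (0.12/0.88) / (0.10/0.90) = 0.1364/0.1111 = 1.23
- p = 0.10, RR = 2.0: (0.20/0.80) / (0.10/0.90) = 0.25/0.1111 = 2.25
- p = 0.30, RR = 1.2: (0.36/0.64) / (0.30/0.70) = 0.5625/0.4286 = 1.31
- p = 0.30, RR = 2.0: (0.60/0.40) / (0.30/0.70) = 1.5/0.4286 = 3.50

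| Control risk | OR at RR 0.5 | OR at RR 1.2 | OR at RR 2.0 | Risk difference at RR 1.2 |
|---|---|---|---|---|
| 0.5% | 0.499 | 1.201 | 2.01 | +0.1 points |
| 3% | 0.492 | 1.207 | 2.06 | +0.6 points |
| 7% | 0.482 | 1.218 | 2.16 | +1.4 points |
| 10% | 0.474 | 1.227 | 2.25 | +2 points |
| 20% | 0.444 | 1.263 | 2.67 | +4 points |
| 30% | 0.412 | 1.312 | 3.50 | +6 points |

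**Relative size of the gap (OR/RR).** At RR 1.2 it is 1.227/1.2, about 2%, at 10% risk, and 1.312/1.2, about 9%, at 30%. At RR 2.0 it is 12.5% and 75%. At 0.5 to 3% risk it is about 3% or less in every scenario.

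**Reverse direction.** With RR = OR / (1 − p + p·OR), a reported OR of 1.2 is an RR of 1.18 at 10% and 1.13 at 30%. An OR of 2.0 is 1.82 and 1.54.

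**Why the planned model does not fill the gap.** The conditional likelihood removes the intercept of each matched set. Without those intercepts the fitted model has no baseline risk, so adjusted absolute risks cannot be recovered from it. They need a separate model.

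**The case against.** The strongest reply is that the protocol contains no error here. Conditional logistic regression is a standard model for matched sets, and section 4.4 gives that reason for it. The protocol never says an odds ratio will be read as a relative risk. Crude risks will be reported as well, and supplementary adjusted measures could sit in an SAP that is not at hand. Much of this stands, and it rules out several stronger readings:

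- A reader might infer that objective 2 goes unanswered. It does not: "To investigate whether the risk of adverse pregnancy, maternal and neonatal outcomes is different in vaccinated pregnant women, compared with unvaccinated pregnant women" names no ratio measure, and for a binary outcome the odds ratio is 1 exactly when the relative risk is 1.
- A reader might infer that the power calculation is invalid because its alternatives are relative risks. A relative risk at a given control risk simply fixes two proportions; no power figure is wrong because an odds ratio is reported.
- A reader might infer that absolute risks are absent or will lack intervals. Section 4.3 plans crude risks by group, which serves objective 1 descriptively, and it is silent on intervals. Silence does not show that there will be none.
- Odds ratios are non-collapsible, so a shift from unadjusted to adjusted value is not purely confounding. But section 4.4 does not say the shift will be read that way, and the effect has not been quantified here.

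The examples also need care. The 30% is for postpartum haemorrhage; the risk of the whole bleeding composite after the clean window is not given. Miscarriage is modelled multinomially against live births or ongoing pregnancies, so its odds ratio is a further step from a risk ratio.

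What the reply does not remove is that section 4.4 itself fixes the measure for each comparison, and nothing the protocol commits to gives an adjusted effect on the risk scale.

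**Conclusion.** The point holds as a modest improvement to reporting. The planned tests remain valid; what is missing is an adjusted effect size on the risk scale of the objectives. The gap is small at 10% risk with a modest effect (RR 1.2 becomes OR 1.23), larger with a strong effect or a commoner outcome (2.25 for RR 2.0 at 10%; 1.31 and 3.50 for RR 1.2 and 2.0 at 30%), and negligible for rare outcomes.

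This rests on Table 2's background risks applying to the matched cohorts, and on a marginal conversion. The planned odds ratios are conditional on matched sets, so the figures are approximate for what the study would report. Nor do the documents require the odds ratio to give up its place as the headline; which measure leads is a trade-off for the study team.

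**What to change.** Keep the odds ratios in section 4.4. In the main matched analyses, add the following.

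- **Hypertensive disorders, small for gestational age, pregnancy-related bleeding and preterm birth:** an adjusted risk ratio and an adjusted risk difference, each with a 95% confidence interval. Use modified Poisson regression with robust variance clustered on matched set, or marginal standardisation using the matching factors and the Table 4 covariates. Standardisation gives both measures from one fitted model.
- **Miscarriage:** standardised risks in each group and their difference, beside the multinomial odds ratio.

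The rare outcomes need no change. The cost is one extra model per common outcome in each main analysis, and longer tables. No new data are needed, and design, matching and sample size are unaffected.

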Pregnant women will be identified through the COPS² study database if they appear on one or more of the data sources listed for the identification of pregnant women in Table 1.

Table 1: Overview of data sources used for analysis

Data	Data source

Datasets required to identify pregnant women in the general population and associated pregnancy start and end dates:
	
 • New national data return developed as part of the response to the COVID-19 pandemic providing information on women booking for antenatal care with NHS maternity services: for identification of women with ongoing pregnancies in near real-time (all other records that identify end of pregnancy events) • GP consultation data: for identification of women with early miscarriage or ectopic pregnancy not managed in hospitals • Scottish Morbidity Record (SMR) 01: for identification of women with early miscarriage or ectopic pregnancy managed in hospitals • Termination of pregnancy statutory notifications (AAS records) • SMR 02: for identification of later miscarriage, stillbirth, and live births managed in hospital (and some home births) • National Records of Scotland (NRS) statutory stillbirth registrations • National Records of Scotland (NRS) statutory live birth registrations • New national data return developed as part of the response to the COVID-19 pandemic providing information on live births notified by maternity services to NHS Board child health administrative departments: for near real-time access to data that allows intergenerational linkage of records relating to mothers and their babies. 
Note that this is already established as part of the COPS study and methodology is set out in the Protocol for estimating the number of COVID-19 vaccinations delivered to pregnant women in Scotland and for describing the uptake and coverage of vaccination in the pregnant population.

Datasets required to identify characteristics of pregnant population
	
 • Covariates of interest include: Maternal age, deprivation score, urban/rurality score, ethnicity, pre-pregnancy clinical vulnerability exc diabetes, diabetes, BMI, smoking status, and linked PCR test data to capture confirmed cases of COVID-19 infection. 
Note that all are available through the COPS study database.

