Maternal pre-pregnancy clinical vulnerability (excluding diabetes)	Clinically extremely vulnerable (on shielding list)	
	Clinically vulnerable (Q-COVID comorbidity excluded diabetes or hypertension)	
	Not clinically vulnerable	
Diabetes	Yes – pre-existing diabetes	If we only have a small number of women that are identified as having diabetes but it is unknown as to whether this is gestational or pre-existing, then we will combine gestational diabetes & unknown diabetes groups.
	Yes – gestational diabetes	
	Yes – diabetes onset unknown	
	No diabetes	
BMI at antenatal booking	Underweight (<18.5) Healthy weight (18.5-<25) Overweight (25-<30) Obese (30-<40) or severely obese (≥40) Unknown	Obese and severely obese will be combined.
Smoking at antenatal booking	Yes - current	
	Yes - former	
	No - never	
	Don't know	

Note: categories will be collapsed as required.

We have considered, but are currently not planning to include, several other covariates. These include parity and pregnancy-related complications other than gestational diabetes. Information on parity is only available on delivery records, negating its inclusion for any of the early pregnancy outcomes, and there are concerns about the quality of these data. Theoretically, pregnancy-related complications (e.g. pregnancy-induced hypertension and pregnancy-related bleeding) could be on the causal pathway between vaccination status and other adverse outcomes so will not be included as potential confounders. However, additional analyses will be conducted as appropriate if we see signals of associations between vaccination and outcomes that might be due to differential vaccination uptake in women with pregnancy-related complications. Gestational diabetes was considered as an exception to this and included as a covariate. This is because pregnant women with gestational diabetes were added to the list of individuals clinically vulnerable and therefore eligible for vaccination in priority risk group 6 early in the vaccination programme (March 2021), possibly leading to high uptake in this group, and the known association between diabetes and many of the outcomes under study.

3.6: Cohort study matching

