First, a model with no covariates will be fitted to calculate the unadjusted OR for the association between vaccination status and each outcomes of interest. Subsequently, we will calculate an adjusted OR for the association between vaccination status and each outcomes of interest, by adding all covariates to the model (Table 4). P-values and confidence intervals will be reported for all models. For some rarer outcomes, we will adjust our modelling approach as required (e.g. re-classification of groupings or removing insignificant covariates). Covariate pairs will be assessed for collinearity before adding to the model. For any covariate pairs that are highly correlated, only the covariate which has the biggest impact on the association between the exposure and outcome will be included in the model.

As previously described (section 3.5.2), analyses will be conducted first looking at the association between having any vaccination and outcomes, and then in sub-group analyses stratified by vaccine classes and individual vaccine types;

- Vaccine type: Pfizer, AstraZeneca, Moderna, Janssen
- Vaccine group: Pfizer and Moderna (mRNA); AstraZeneca and Janssen ((adeno)virus vector)
- Number of vaccine doses

Our main analyses will include all pregnancies/births, regardless of whether there is evidence that it was singleton or multiple, with sensitivity analyses conducted restricting to only pregnancies/births where there was no evidence it was a multiple. We often do not know whether pregnancies which end early (e.g. due to miscarriage) were singleton or multiple, hence the decision to only include pregnancies with *no evidence* of being a multiple in these sensitivity analyses.

4.5: Additional analyses

There are two further analyses that may subsequently be conducted to assess the association between vaccination and adverse outcomes, specifically:

1. We will consider using all data from the pre-pandemic period to predict the expected number of outcomes among the vaccinated pregnant women, and compare this predicted number to the observed number within the vaccinated group of women.
2. For rarer outcomes (e.g. for congenital anomalies, microcephaly), we will consider a nested case control study if signals are identified in this present matched cohort analysis but wide confidence intervals due to the small number of events negate any meaningful conclusions. This design maximises power to assess any association between vaccination and these rare outcomes.

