5.0 Potential limitations

There are a number of limitations that need to be considered when conducting the analysis and interpreting the results. Some of the key limitations are as follows:

1. Lag in data becoming available for women recently captured within the COPS study database:
Due to the way the COPS cohort is derived, there is a lag of up to three months before conceptions are identified and hence the corresponding pregnancies included in the study dataset. This is because either antenatal booking, or an early spontaneous pregnancy loss or termination of pregnancy prior to booking, must occur, and the relevant record be returned to PHS, prior to the pregnancy being identified and the conception retrospectively imputed. These events will usually occur within three months of conception. The COPS cohort is refreshed monthly: more frequent refreshes are not feasible as key source datasets (in particular SMR02) are only updated monthly. This means that, using any month's COPS cohort plus up-to-date vaccination data, will likely fail to identify some recent vaccination events as occurring during early pregnancy. These will be picked up in subsequent months as the COPS cohort is refreshed. This means that initial data outputs must be understood as provisional.
2. Capture of early pregnancy loss:
Women who have early pregnancy loss and do not seek medical advice will not be captured in the COPS dataset.
3. Insufficient sample size for rare outcomes:
For rarer outcomes, there may be insufficient power to assess the association between vaccination status and the outcome using a matched cohort study design. We will still provide descriptive data for these outcomes and, as mentioned in Section 4.5, we will consider different analytical approaches for rare outcomes.
4. Missing data:
For some covariates, there will be missing data, but this is expected to be minimal based on ongoing assessments of data quality.
5. Recording errors:

There may be errors in recording the pregnancy, maternity or neonatal outcomes and the way in which outcomes are recorded may have changed over time.

6. Unmeasured confounding:

There is the potential for unmeasured confounding given the inherent differences between vaccinated and unvaccinated women which might not be accounted for. Specific examples include occupation, specific comorbidities, and wider healthcare seeking behaviours including engagement with antenatal care.

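### Booking BMI and smoking are fixed in the adjusted models for early pregnancy loss, although pregnancies lost before booking cannot have a booking value

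*Protocol*

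**What the plan says.** Section 4.4 states the adjustment rule without exception by outcome: "we will calculate an adjusted OR for the association between vaccination status and each outcomes of interest", obtained "by adding all covariates to the model (Table 4"). Table 4 lists "BMI at antenatal booking", with an *Unknown* level, and "Smoking at antenatal booking", with a *Don't know* level.

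Section 5.0, item 1, describes entry to the cohort: "either antenatal booking, or an early spontaneous pregnancy loss or termination of pregnancy prior to booking, must occur". Table 1 finds early miscarriages and ectopic pregnancies from GP consultation data and SMR01. Under section 4.4 the reference outcome is live birth, or ongoing pregnancy at a relevant gestation for early outcomes.

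Section 3.5.3 omits parity. One of its two reasons is availability: "Information on parity is only available on delivery records, negating its inclusion for any of the early pregnancy outcomes". The other is data quality. Section 5.0, item 4, says: "For some covariates, there will be missing data, but this is expected to be minimal".

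**The concern.** A pregnancy that ended before booking has no booking measurement by definition, while a live birth or ongoing pregnancy usually has one. In a model for early loss, the missing level of BMI or smoking is then less a property of the woman than a marker that the outcome has happened. Entering it as an ordinary covariate level conditions on something downstream of the outcome.

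Miscarriage and ectopic pregnancy are both primary outcomes in Table 2, and the primary comparison is between eras. The adjusted odds ratio loses precision in any case. It can also move in either direction if records of early loss are more complete in one era than in the other. In a safety study that could create a signal or hide one.

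**Working it through.** The protocol gives no figure for this point, so there is none to reproduce. The check is a reading of the text followed by an illustration.

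**Inputs from the protocol:** 5,000 vaccinated women and 15,000 controls (section 3.7); 10% loss, the lower end of Table 2's 10-20% for miscarriage; 1% for ectopic pregnancy (Table 2).

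**Assumptions, not in the protocol:** 3% unknown in continuing pregnancies unless stated; 20% to 90% of losses unknown. Matching and the other covariates are ignored.

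**1. How strongly the missing level tracks the outcome.** With 60% of losses and 3% of continuing pregnancies unknown, the odds ratio linking *Unknown* to loss is (0.60/0.40)/(0.03/0.97) = 48.5.

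**2. Missingness depends on the outcome only, equal in both groups.** The vaccination odds ratio stays at 1.00 within each level and overall. Under the null, the information on its log in a level with L losses and C continuing pregnancies is 0.25 × 0.75 × LC/(L+C). Hence

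variance ratio = [LC/(L+C)] ÷ Σ[LₘCₘ/(Lₘ+Cₘ)], summed over the known and unknown levels.

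With L = 2,000 and C = 18,000 the numerator is 1,800. Continuing pregnancies split into 540 unknown and 17,460 known.

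- 20% of losses unknown: 400×540/940 + 1,600×17,460/19,060 = 229.8 + 1,465.7 = 1,695.5; ratio 1.06.
- 30%: 600×540/1,140 + 1,400×17,460/18,860 = 284.2 + 1,296.1 = 1,580.3; ratio 1.14.
- 60%: 1,200×540/1,740 + 800×17,460/18,260 = 372.4 + 765.0 = 1,137.4; ratio 1.58. The standard error goes from 0.054 to 0.069.

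For ectopic pregnancy at 1% (L = 200, C = 19,800, numerator 198) with 60% unknown: 120×594/714 + 80×19,206/19,286 = 99.8 + 79.7 = 179.5; ratio 1.10. The precision cost is smaller there.

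**3. Completeness also differs between groups, true odds ratio 1.00.** The model in section 4.4 fits one vaccination odds ratio across the known and unknown levels. Two worked cases on expected counts:

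- 90% of control and 70% of vaccinated losses unknown. Known level: (150×13,095)/(4,365×150) = 3.00. Unknown level: (350×405)/(135×1,350) = 0.78. Without the indicator: (500×13,500)/(4,500×1,500) = 1.00.
- 70% of losses unknown in both groups, but 4% of continuing controls and 2% of continuing vaccinated women unrecorded. Known level: (150×12,960)/(4,410×450) = 0.98. Unknown level: (350×540)/(90×1,050) = 2.00.

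Logistic regression on the expected counts with the *Unknown* indicator gives:

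| Unknown, controls v vaccinated | Fitted OR (truth 1.00) |
|---|---|
| losses 60% v 55% | 1.06 |
| losses 70% v 65% | 1.07 |
| losses 80% v 75% | 1.09 |
| losses 90% v 85% | 1.13 |
| continuing 4% v 2%, losses 70% in both | 1.27 |
| losses 90% v 70% | 1.56 |
| losses 60% v 80% | 0.78 |

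**4. A related route.** If vaccination raised only pre-booking loss, 1.5-fold, with 70% of losses before booking and 2% unrecorded among booked pregnancies, total loss in the vaccinated would be 10.5% + 3% = 13.5%. The odds ratio without the indicator is (0.135/0.865)/(0.10/0.90) = 1.41; with it, the fitted value is 1.20.

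**The case against.** The best defence is that bias has not been shown. Missingness driven by the outcome alone leaves the odds ratio intact, and the larger distortions need gaps of 20 points that nothing in the protocol supports. That stands.

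A reader might infer an era difference from Table 1, which lists a "New national data return developed as part of the response to the COVID-19 pandemic providing information on women booking for antenatal care". The document does not support that step. The return appears in the row for identifying pregnancies, and it is not named as the source of BMI or smoking. Those sit in a separate row, which says only that the covariates are available through the study database.

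A reader might also infer that no miscarriage can carry booking values. Miscarriage runs to 23+6 weeks, and section 5.0 says booking or early loss usually occurs within three months of conception, so most second-trimester losses should follow booking. The parity parallel is partial too: parity was dropped for two reasons, and from every model. It is also inferred, not stated, that unbooked pregnancies fall into smoking's *Don't know* level.

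There are partial safeguards. Unadjusted odds ratios are reported, outcome risks are tabulated by covariate, and controls are matched on gestational week at the vaccination date. The first two could expose a shift, but they do not say which estimate to believe.

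The flexibility in section 4.4 does not solve the problem. It is meant for rarer outcomes, and miscarriage at 10-20% is not one. It removes insignificant covariates, and a level this closely tied to loss would be highly significant. The collinearity rule keeps whichever covariate moves the association most, which could be the more distorting one. Nor is this simply a detail left for an analysis plan, because the protocol itself fixes the covariate list for every outcome.

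**Conclusion.** The concern holds as a flaw in the stated adjustment rule. For first-trimester miscarriage, ectopic pregnancy and the early part of overall miscarriage, the missing level of booking BMI and smoking is largely produced by the outcome.

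The expected consequence is lost precision. At 10% loss it is modest if 30% of losses are unknown and substantial if 60% are; for ectopic pregnancy it is smaller. Bias is possible but conditional: it needs completeness, or the timing of loss, to differ between vaccinated women and pre-pandemic controls. For gaps of a few points it would be small (about 1.06 to 1.13). It would matter for an uneven recording rate among continuing pregnancies (1.27) or a large gap among losses (1.56), and it can run in either direction. The stronger statement, that the adjusted odds ratio for these outcomes is biased, goes beyond what the protocol shows.

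All sizes rest on assumed missingness and on a model without matching. What does not rest on assumption is that limitation 4 cannot be right for pre-booking losses, where booking values are absent by definition.

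**What to change.** In section 4.4, state that the adjusted models for overall miscarriage, first-trimester miscarriage and ectopic pregnancy omit booking BMI and smoking, or use only pre-conception values available in both eras. Keep both covariates for second-trimester miscarriage and for later outcomes, where they are largely measured.

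Add to section 4.3 a table of BMI and smoking missingness by outcome and study period. Qualify limitation 4 so that its expectation of minimal missingness excludes losses before booking.

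This takes a few sentences and one table. The price is some residual confounding by BMI and smoking for the early-loss outcomes, including among post-booking losses in the overall miscarriage model, where the values were measured.
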